**Table 3. Site Descriptions, Current Need and Provision of Addiction Treatments**

Site	Miriam Immunology Center	Boston Medical Center	Hartford Hospital	Downstate
Number of HIV-infected receiving care	1600	1200	500	1200
Number with untreated Tobacco Use Disorder	400	300	200	425
Number receiving on-site medication for tobacco use disorder (bupropion, NRT, varenicline)	140	Unknown	75	110
Number receiving on-site counseling for tobacco use disorder	Unknown	Unknown	50	7
Number with untreated Unhealthy Alcohol Use	100	200	75	240
Number receiving on-site medication for unhealthy alcohol use (naltrexone, acamprosate, disulfiram)	0	16	0	0
Number receiving on-site counseling for unhealthy alcohol use	Unknown	16	0	100
Number with untreated Opioid Use Disorder	80	100	80	100
Number receiving on-site medication for opioid use disorder (buprenorphine, naltrexone)	32	50	0	4
Number receiving on-site counseling for opioid use disorder	32	50	0	7

## Formative Evaluation (Aim 1)

### Overview of Formative Evaluation

We will conduct a three-stage formative evaluation using mixed-methods (qualitative and quantitative) to identify evidence, context, and facilitation-related factors impacting the provision of addiction treatments and use these data to tailor, refine, monitor and evaluate the effectiveness of the Implementation Facilitation. Given that formative evaluation techniques will be used in advance, during and following Implementation Facilitation, we will describe the methods in detail here and refer back to this section as needed.

Formative evaluation is a widely accepted implementation assessment approach designed to identify influences on the development, progress and effectiveness of implementation efforts. To increase use of addiction treatments, we will use this formative evaluation to understand: 1) site-specific practices, 2) determinants of these practices, 3) barriers and facilitators to practice change, and 4) perspectives regarding Implementation Facilitation. Using the PARiHS framework, we will employ a mixed-methods approach with 1) quantitative methods, using the Organizational Readiness to Change Assessment (ORCA) followed by 2) qualitative methods to develop an understanding of evidence, context and facilitation-related factors impacting the provision of addiction treatments from the perspectives of diverse stakeholders including patients, nurses, social workers, physicians, NPs, PAs, pharmacists, psychologists, clinic administrators, payers and clinic directors.

### Eligibility for Participation in Formative Evaluation:

**Patients:** HIV-infected; age  $\geq 18$  years old; meets criteria for lifetime or current tobacco, and/or alcohol and/or opioid use disorder regardless of addiction treatment status; able to provide verbal informed consent.

**Clinic Staff, Administrators:** employed at participating HIV clinic for at least six months.

**Payers:** employed at an organization or agency that provides funding for medical services for HIV-infected individuals for at least 6 months.

### Quantitative Data Collection and Analysis

We will use the ORCA, a 77-item instrument based on the PARIHS framework, to evaluate evidence, context and facilitation-related factors impacting implementation of addiction treatments in each of the four HIV clinics. Baseline ORCA scores will be used to determine evidence, context and facilitation-related strengths and weaknesses in organizational readiness to implement addiction treatment and to tailor the Implementation Facilitation.

### Qualitative Data Collection and Analysis

We will conduct focus groups with a purposeful sample of key stakeholders at three distinct stages of our project: the planning phase, implementation phase and evaluation phase. Purposeful sampling is a well-established method in qualitative studies and is designed to identify study participants who have direct experience with or knowledge of the phenomenon of interest, in this case substance use disorders and addiction treatment. We will ensure appropriate breadth of samples with regard to salient characteristics that may influence participant views on the topics of interest. We have chosen to use focus groups given their suitability for generating data from multiple perspectives regarding the organizational and individual level factors impacting complex processes whereby the group interaction is anticipated to stimulate unique ideas. We will enroll patients, nurses, social workers, physicians, NPs, PAs, pharmacists, psychologists, clinic administrators, payers and clinic directors at each site to allow for evaluation of processes from multiple perspectives (triangulation). Focus groups will be conducted at each site with 8-10 patients with past or current tobacco, alcohol and/or opioid use disorders and 8-10 staff members and payers, with at least one individual from each of the stakeholder categories. We will conduct focus groups until we reach thematic saturation.

**Development of focus group questions:** The focus group guides will be informed by the PARIHS framework and include “grand tour” questions designed to establish rapport and elicit open-ended responses. Probes will be used to understand specific details of those experiences and allow for clarification of ideas. We will design and pilot test these guides with patients and key informants from the New England HIV Implementation Science Network and refine as indicated.

**Conduct of focus groups:** [name], in conjunction with a trained research assistant, will conduct focus groups at each site during year 1 (planning phase), year 2-3 (implementation phase) and year 4 (evaluation and maintenance phases). The focus groups will be recorded and professionally transcribed for qualitative analysis. Participants will also complete a brief anonymous demographic survey. Using directed content analysis, we will analyze the data with a multi-disciplinary group with experience in qualitative methods, which will include HIV

and Addiction Medicine physicians, a HIV Clinic Director, a Clinical Psychologist, and a health service researcher. Data will be entered into and organized using Atlas.ti software.

We will share our results with participants (participant confirmation) to ensure that we have accurately understood and represented stakeholder’s perspectives and experiences. We will use data reduction strategies to sharpen, sort, focus, discard and organize data in a way to draw inferences regarding the implementation interventions in place at each facility. We will develop a template summary of data at each facility organized by evidence, context and facilitation-related factors. Once we have developed that summary for each site, we will create a matrix across all sites and respondents to understand the major issues with regard to implementation across sites. These data will directly inform the site-specific Implementation Facilitation and be used to evaluate the facilitation process and outcomes.

**Description of the implementation strategy**

Overview of the Implementation Facilitation (See Table 2)

Implementation Facilitation will be based on a manualized program developed by Kirchner and colleagues that has had significant impact on implementing healthcare practices in clinical settings. Building on the mixed-methods analysis conducted in Aim 1, we will use the PARIHS framework to tailor the Implementation Facilitation for site-specific needs. The facilitators and barriers identified by administrators, providers, and patients and will be characterized according to the PARIHS sub-elements of patient and clinical experience (communication, knowledgeable and empathetic providers), receptive context (resources to provide addiction treatments), and culture (value of team-based approach) identified. As described below, PARIHS will be used to further explicate and design the Implementation Facilitation, guide the ongoing formative evaluation and revise the strategy in an iterative manner to improve implementation success. The individual components (Table 2) of Implementation Facilitation are described below.

**Table 2. Components of Implementation Facilitation**

Component	Description
External Facilitator	Outside content expert who assists site
Local Champion	Local site stakeholder who promotes change
Provider Education and Academic Detailing	Provision of unbiased peer education
Stakeholder Engagement	Aligning goals of implementation and those impacted
Tailor Program to Site	Addressing site specific needs based on Aim 1
Performance Monitoring and Feedback	Assess implementation of screening and treatment efforts and inform site of results
Formative Evaluation	Quantitative and qualitative determination of impact
Establish a Learning Collaborative	Shared learning opportunities tailored to stakeholders
Program Marketing	Efforts designed to increase attention to availability of on-site addiction treatment services

Components of Implementation Facilitation

**External facilitator** - [name] will provide training, coach and mentor local champions, and encourage the exchange of ideas within and among sites.

**Local champions** - [name] will spend the first year of the project working with the local site PIs to identify and engage local champions, including physicians, clinic directors, pharmacy or nursing leads or local organizational re-design/quality improvement experts. These

individuals, and their current level of involvement in the HIV clinic, will likely vary by site and substance. Following the in-person orientation and trainings, [name] will provide external facilitation including monthly phone meetings for the six months of the Implementation Facilitation. The Project Coordinator will take notes during these meetings, capturing information on challenges, barriers, facilitators and strategies. This information will be integrated into the formative evaluation.

**Provider education and academic detailing** - Academic detailing involves trained clinician consultants visiting other clinicians to share unbiased information about patient assessment and treatment with the goal of improving quality of care. All providers involved in the implementation will have dedicated educational sessions on addiction treatments specifically tailored to each provider's tasks based on the initial formative evaluation and potentially modify, remove or add strategies to enhance implementation. We will address practical issues such as efficient use of the electronic medical record, public, private and AIDS Drug Assistance Program payment for treatments, and patient monitoring strategies. We will share protocols for integration that have been developed for integration of buprenorphine and naltrexone at the Yale HIV clinics and elsewhere. Drs. [name], [name], [name], and [name] will be primarily responsible for providing the content or identifying local site content experts who can deliver interactive training sessions. Training strategies will be based on adult learning theory and include didactic presentations on the effectiveness and safety of addiction treatment and skill's based practice sessions. These sessions will focus on 1:1 and small group activities to promote the education of providers regarding the use of motivational interviewing, brief interventions, addiction counseling and medications. We will focus on frequent brief presentations at provider meetings, lectures with meals/refreshments and provide instructional handouts.

**Stakeholder engagement** will take place at the administrative, provider, and patient level. Efforts at increasing engagement will be informed by the focus groups conducted during the initial formative evaluation and supported by the efforts of the local champions. This work will be informed by the Normalization Process Model whereby the external facilitators will work to make attention to tobacco, alcohol and opioid use disorders a routine focus of stakeholders (e.g. embedded) and processes are developed whereby practices such as routine screening and medication use are sustained and routinely monitored.

**Tailoring the program to local site** will occur as a result of the formative evaluations and will be informed by local site PIs and local champions.

**Performance monitoring and feedback** - This will involve regular assessment of individual clinician performance and providing information about that performance. We will work with clinic directors and other members of the clinic team to identify the optimal outcomes to be tracked as well as how often and in what format feedback will be provided based on clinic and provider-level data. Outcomes will include the number of screenings performed, prescriptions of addiction medications provided or number of sessions of the counseling provided. [name] in collaboration with Drs. [name] and [name] will provide additional training or educational booster sessions for sites with low implementation and those requesting such services.

**Implementation-focused formative evaluation** will occur during the implementation and focus on the discrepancies between the implementation plan and its operationalization. Examples of processes that will be examined include: 1) number and types of educational trainings attended by staff, 2) number of staff who view the audit and feedback reports, and 3) number of champions that attend facilitation meetings.

**Progress-focused formative evaluation** meetings, led by [name], will monitor achievement of implementation goals and performance targets to identify blocked progress, allowing steps to be taken to optimize the intervention. These meetings will focus on barriers and strategies to address identified barriers. Non-attendance of site participants will be documented and outreach through individual facilitation meetings, calls or emails will be initiated to assess for stalled progress and offer assistance.

**Interpretive formative evaluation** uses the data collected from the other formative evaluations and information collected at the end of the project regarding the participant experiences to clarify the meaning of successful or failed implementation and to enhance understanding of Implementation Facilitation's impact. At the conclusion of the maintenance phase (12 months), we will conduct an interpretive evaluation that will assess stakeholder views regarding (a) value of each addiction treatment, (b) satisfaction or dissatisfaction with various aspects of Implementation Facilitation, (c) reasons for clinic level action or inaction, (d) additional barriers and facilitators, and (e) recommendations for further refinements. Information will also assess stakeholders' beliefs regarding Implementation Facilitation's success and overall "worth".

**A Learning Collaborative** will be formed by inviting each of the sites' local champions, and other key stakeholders, to participate in a monthly call to promote shared learning regarding issues promoting and hindering implementation of addiction treatment. The local champions and key stakeholders will set the agenda and the calls will be facilitated by [name] and [name] and provide a dedicated time to discuss site-specific updates, challenges and possible solutions for implementation of addiction services. [name] will make resources, protocol templates, materials and presentations available through the New England HIV Implementation Science Network and other websites so they will be widely accessible.

**Program Marketing** will be conducted to promote awareness among patients and providers in the clinics of the availability of on-site addiction treatment services. This will include dissemination of promotional materials such as "What if? Ask me!" buttons, flyers, pens, pads and sticky notes for all clinic staff (Appendix for examples from current studies). The goal of the marketing will be to promote screening and treatment. We will emphasize patient motivation in this process. While the efficacy of addiction treatment is clear, most research is conducted on motivated patients seeking treatment for their addictive disorders. Our experience conducting research in HIV clinics and general medical settings demonstrates that patient motivation to address their addictive disorder is often very low, especially when their disorder is detected during a routine visit for a general medical condition. This means that it will be imperative for our efforts to increase treatment of addictive disorders in HIV settings to address patient motivation. Our "What if? Ask me!" slogan is designed to initiate a motivational discussion between patients and providers. The ultimate marketing approach will be tailored to the needs of the stakeholders and include direct (e.g. "in-services" to discuss the treatment

services and referral processes, flyers) and indirect (e.g. informal conversation) approaches. We will distribute a newsletter every six months to provide updates about the “WHAT IF?” program across the sites.

Please note that these materials will not be designed until April 2016. At that time, an amendment will be submitted to the IRB for approval.

### **Evaluating the Effectiveness of the Implementation Facilitation (Aim 2 and Aim 3)**

#### Overview

We will use a stepped wedge design (Table 4) to evaluate the effect of the Implementation Facilitation on the outcomes. In a stepped wedge design, clinics are randomly assigned to time cohorts and then followed prospectively to determine their outcome status. Stepped wedge designs are increasingly used to promote the implementation of evidence-based practice and are appropriate for evaluating interventions where there is evidence that the intervention is likely to be beneficial and when practical considerations require sequential deployment of an intervention. We will have three phases of six-months each: 1) a pre-implementation control period, 2) a post-intervention evaluation period, and 3) a maintenance period. The proportion of eligible patients in each time period who receive at least one addiction treatment will be assessed and the effect of the intervention will be evaluated by comparing pre-implementation to evaluation and maintenance periods. This will allow us to assess the short and long-term (maintenance) impact of Implementation Facilitation.

**Table 4. Overview of clinic phases the stepped wedge study design (IF = Implementation Facilitation)**

Clinic 1	Control	Control	Control	Control	IF	Evaluation	Maintenance
Clinic 2	Control	Control	Control	IF	Evaluation	Maintenance	Maintenance
Clinic 3	Control	Control	IF	Evaluation	Maintenance	Maintenance	Maintenance
Clinic 4	Control	IF	Evaluation	Maintenance	Maintenance	Maintenance	Maintenance

We will measure a range of implementation variables at baseline, 6 and 12 months (Table 5). Using validated instruments before, during and after Implementation Facilitation we will examine the impact of Implementation Facilitation on organization readiness, provider readiness, treatment provision, models of care and HIV outcomes. For sample size calculation, the primary quantitative outcome, assessed six and 12 months after the Implementation Facilitation is completed, will be the proportion of eligible individuals receiving addiction treatments from the clinic measured using information derived from the electronic medical record. This determination will be conducted in a blinded fashion, such that the individual analyzing the electronic medical record data will be unaware of the phase (control, evaluation, maintenance) of the Implementation Facilitation. Secondary quantitative outcomes, assessed at six and 12 months will be change in organizational readiness measured using the ORCA, change in provider readiness to prescribe addiction medications measured using change rulers, and HIV-related outcomes. To facilitate data collection, all surveys will be administered to all stakeholders online using the survey software, Qualtrics and collected anonymously.

**Table 5. Summary of Study Assessments**

Assessment	Data Source	Baseline Control	6 months Evaluation	12 months Maintenance
Organizational Readiness to Change Assessment	Provider and Organizational representatives	X	X	X
Change Rulers for each medication and counseling intervention	Provider and Organizational representatives	X	X	X
Conduct of screening for each condition	Electronic Medical Record	X	X	X
Use of each medication and counseling intervention	Electronic Medical Record	X	X	X
Patient demographic information	Electronic Medical Record	X	X	X
Receipt of antiretroviral therapy	Electronic Medical Record	X	X	X
Tobacco, Alcohol and Opioid Use Disorders	Electronic Medical Record	X	X	X
Psychiatric Diagnoses	Electronic Medical Record	X	X	X
Clinic Visits	Electronic Medical Record	X	X	X
Laboratory values	Electronic Medical Record	X	X	X
Receipt of benzodiazepines	Electronic Medical Record			X
Receipt of COVID-19 screening and COVID-19 diagnosis	Electronic Medical Record			X

Adequacy of sample size

Based on prior work, we anticipate that Implementation Facilitation will increase the proportion of eligible patients provided addiction treatment by the clinics from a baseline of 15% of eligible patients (Table 3) to 26% during the evaluation phase and 33% during the maintenance phase. This reflects an 11% absolute increase (75% relative increase) during the evaluation phase and a 19% absolute increase (125% relative increase) during the maintenance phase. A parallel group design, unadjusted for clustering and repeated measures would require a sample size of 592 (296 in each the control and intervention arms) to detect the estimated effect size (15% control vs. 26% intervention; power 90% and Type I error (alpha) of 0.05). We used the formula of Woertman et al. to incorporate the effect of the stepped wedge design. It was assumed that each clinic would provide a minimum of 300 addiction treatment eligible patients (n). In addition, the following assumptions were used, intracluster correlation,  $\rho = 0.01$ , number of steps,  $k = 4$ , number of baseline measurements,  $b=1$ , number of measurements taken after each

step,  $t=1$ . With the above assumptions, the derived  $DE_{sw} = 0.63$ , thus yielding an adjusted sample size of 375 across the 4 clinics. This yields a sample size for the initial evaluation phase of 94 patients per clinic who are eligible for addiction treatment (tobacco, alcohol or opioid use disorder). Three primary time points will be used, control (six months) evaluation (six months) and maintenance (six months). Given we will have adequate power to detect a difference of a 11% increase in the provision of addiction treatments in the evaluation phase, we will be adequately powered for the 19% increase anticipated during the maintenance phase and for the other quantitative analyses proposed in Aims 2 and 3. This sample size estimated above is based on a ‘cross-sectional’ design. Even if the population in the clinics/clusters is assumed to be a stable ‘cohort’, the power will likely be more than sufficient due to within-patient correlation.

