**Analysis for Aim 2a, 2b, and 2c:** Number (percent) will be used to present data from categorical variables. Continuous variable data will be presented as means (+/- SD) and those with a non-normal distribution will be characterized using medians (interquartile range). Differences across the clinics will be assessed using appropriate parametric or non-parametric techniques. The provision of addiction treatments among those eligible (Aim 2c) will be expressed as a percentage and the distribution of results in the control (unexposed) periods will be compared with those in the evaluation (exposed) and maintenance (exposed) periods. Characteristics of patients and clinics will be shown by randomization status in each step of the design. We will conduct similar analyses for the measures of organizational and provider readiness (Aims 2a, 2b) where the dependent variable will be expressed as continuous measures (ORCA score and change rulers). Based on the PARIHS, we hypothesize that stakeholder scores on the ORCA subscales including clinical experiences, patient preferences, leadership culture

and measurement will mediate the proportion of patients receiving addiction treatment. We will test the relationship among this outcome and these mediators. To test the significance of the mediation effect, which is called the indirect effect, we will calculate Sobel's test for each proposed mediator. We will use an intent-to-treat approach (i.e. cluster analysis will be done) according to the time clinics were intended to cross over from control to Implementation Facilitation. A linear mixed model will be used, adjusting for calendar time (a potential confounder due to its association with both exposure to the intervention and outcome), with a random effect for clinic, a fixed effect for each step and allowing for repeated measures for patients in the clinics. Since the population of the clinics participating in the proposed trial will be rather stable, thus rendering this a cohort stepped wedge design, an additional random effect for patients in each clinic will be introduced.

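### The 94 patients per clinic was sized for a five-period wedge; in the seven-period Table 4 design, with the facilitation periods left out, 94 per clinic-period gives about 76% power rather than 90% (99.6% at the assumed 300)

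*Combined protocol and SAP*

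**What the plan says.** **Sample size** (Section V, Adequacy of sample size). Treatment provision is expected to rise "from a baseline of 15% of eligible patients (Table 3) to 26% during the evaluation phase" and to 33% in maintenance. A parallel-group size of 592 (296 per arm, 90% power, alpha 0.05) is multiplied by a stepped-wedge design effect of 0.63. The inputs are ICC 0.01, k = 4 steps, b = 1 baseline measurement, t = 1 measurement after each step, and n = 300: "It was assumed that each clinic would provide a minimum of 300 addiction treatment eligible patients". The product is 375, and the conclusion is "This yields a sample size for the initial evaluation phase of 94 patients per clinic who are eligible for addiction treatment". Sampling is taken as cross-sectional. The section then adds: "Three primary time points will be used, control (six months) evaluation (six months) and maintenance (six months".

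**Design** (Table 4). Four clinics are followed over seven periods. Each clinic has one to four control periods, then one IF period, one evaluation period and one to four maintenance periods.

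**Comparison.** The overview of the effectiveness evaluation says "the effect of the intervention will be evaluated by comparing pre-implementation to evaluation and maintenance periods". The analysis for Aims 2a to 2c says "the distribution of results in the control (unexposed) periods will be compared with those in the evaluation (exposed) and maintenance (exposed) periods", with adjustment for calendar time, a random clinic effect and a fixed effect for each step. The same paragraph defines intent-to-treat "according to the time clinics were intended to cross over from control to Implementation Facilitation".

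**The concern.** With k = 4, b = 1 and t = 1 the formula covers b + kt = 5 periods, an immediate move from control to exposed, and a single exposed effect. Table 4 has seven periods, a separate IF period between control and evaluation, and two exposed phases.

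The comparison sentences put IF periods on neither side. The intent-to-treat sentence could put them on the exposed side. No section says how they are coded, and the required size depends on it.

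The plan uses the adequacy of this size to claim adequate power for maintenance and for the other quantitative analyses in Aims 2 and 3. If the size falls short for the design actually drawn, that inference loses its basis.

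Two further points bear on the same calculation:

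- **Which periods are extracted.** The sentence on three primary time points, and the three columns of Table 5, can be read as one window per phase at each clinic. The plural periods and the step effects in the analysis section point to using all of them.
- **The baseline.** The 15% cites Table 3. That table has a column for Boston Medical Center, which is not in the site list, and none for the Haelen Center, which is. Several cells are unknown, and the counts are by condition rather than by patient.

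**Working it through.** **Step 1. Reproduce the plan's figures.**

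- Two proportions, two-sided 0.05 (sidedness is not stated), 90% power: n = (1.960 + 1.282)² × (0.15×0.85 + 0.26×0.74) / 0.11² = 277.8 per arm. With continuity correction this is 295.7, so 296 per arm and 592 in total.
- Design effect = [1 + ρ(ktn + bn − 1)] / [1 + ρ(ktn/2 + bn − 1)] × 3(1 − ρ) / [2t(k − 1/k)] = (1 + 0.01×1499)/(1 + 0.01×899) × (3×0.99)/7.5 = 1.601 × 0.396 = 0.634.
- 592 × 0.634 = 375, and 375/4 = 94. The stated chain is arithmetically correct.

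**Step 2. Power for a given layout.** Generalised least squares on clinic-period means, with fixed calendar-period effects and a random clinic intercept:

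- Mean proportion (0.15 + 0.26)/2 = 0.205, so total variance is 0.205 × 0.795 = 0.163. With ICC 0.01, the between-clinic variance is 0.01 × 0.163 and the within-clinic variance 0.99 × 0.163.
- For clinic i with n patients per period, V_i = (between-clinic variance) × J + (within-clinic variance / n) × I, where J is the all-ones matrix and I the identity. The SE is the square root of the relevant diagonal element of (Σ X_i′ V_i⁻¹ X_i)⁻¹.
- Power = Φ(effect/SE − 1.96).

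The 94 is read as per clinic-period, which favours the plan. Spread over all seven periods it would be 13.4 per period, with power about 19%.

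**Step 3. Results for the 11-point evaluation effect.**

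| Layout | SE at 94 | Power at 94 | n per clinic-period for 90% | Power at 300 |
|---|---|---|---|---|
| Five-period wedge (the formula's inputs) | 0.0320 | 93% | 83 | – |
| Table 4, IF periods left out (28 − 4 = 24 cells) | 0.0414 | 76% | 143 | 99.6% |
| Table 4, IF periods kept with their own term | 0.0390 | 80.5% | 127 | 99.8% |
| Table 4, IF coded as exposed (full effect assumed during IF) | 0.0308 | about 95% | 77 | – |

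For the second row: 0.11/0.0414 − 1.96 = 0.70, and Φ(0.70) = 0.76. At 300 the SE is 0.0237, so 0.11/0.0237 − 1.96 = 2.68 and power is 99.6%. Coding IF as control, with no effect assumed during IF, also gives about 95% at 94.

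Maintenance contrast (15% versus 33%, 18 points), IF left out: SE 0.0535 and power 92% at 94; SE 0.0311 and power above 99.9% at 300.

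**Step 4. Sensitivity of the 76%** (Table 4, IF left out, 94 per clinic-period).

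- ICC 0.005, 0.02, 0.05 and 0.10: 77%, 75%, 75% and 77%.
- Linear instead of categorical time: 85%, with 112 needed.
- Cohort sampling, with an assumed 25% or 50% of patient-level variance persisting: 86% or 96%.
- Assumed baseline of 10%, 15%, 20% or 25% with the same 11-point rise: 84%, 76%, 69% or 64%. The sizes needed are 114, 143, 168 and 188, and power at 300 is at least 98% throughout.

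**Step 5. One window per phase, if the text is read that way.**

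- Control window just before IF, separate evaluation and maintenance effects: 53% at 94 and 73% at 300. With one constant effect: 54% and 84%.
- Common first-period baseline: the effect is not estimable with categorical periods. With linear time, power is 34% at 94 and 71% at 300.

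**The case against.** The strongest reply concerns materiality. The plan's minimum is 300 eligible patients per clinic; 94 is only a derived requirement. Outcomes are read from records and nothing caps the number at 94. At 300 per clinic-period, power is 99.6%. Every site tabulated in Table 3 has at least 200 patients with untreated tobacco use disorder alone, and 200 per clinic-period would give 96.8%. This stands: the trial as intended is not short of patients. Two limits remain. The protection requires all control, evaluation and maintenance periods to be extracted, and Table 3 has no entry for the Haelen Center.

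A second reply is that the analysis treats the clinics as a cohort with a random patient effect, which raises power. That also stands in part: at 94 the figure reaches 90% if about 35% of patient-level variance persists. But the plan gives no within-patient correlation and says its own calculation is cross-sectional.

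Third, the one-window reading is not the natural one. The analysis section's plural periods and step effects favour using all cells, so the figures in step 5 are conditional and not the main finding.

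Fourth, the power figures use normal quantiles with only four clinics and no clinic-by-period variation, so they are approximate. Allowing for either would lower power rather than restore it. The Table 3 mismatch is a separate inconsistency, but it affects the baseline used here.

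**Conclusion.** The concern holds. The required size of 94 per clinic does not deliver the stated 90% for the Table 4 design when IF periods are left out, as the comparison sentences imply. Power is about 76%, and about 143 per clinic-period are needed (127 if IF periods carry their own term). The coding of IF periods, which the plan does not state, moves power at 94 from 76% to about 95%.

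The practical risk is limited: at the assumed 300 per clinic-period, power is 99.6% for the evaluation contrast and above 99.9% for maintenance. The sample-size statement should be corrected, but the design does not fail.

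These figures rest on the plan's ICC of 0.01, cross-sectional sampling and 15% versus 26%. They also rest on a two-sided test, categorical calendar periods, normal quantiles and reading 94 as per clinic-period, which are assumptions made here. The true baseline for the four listed sites is unknown.

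**What to change.** 1. State which cells are analysed. For example: *The primary outcome from the electronic medical record is extracted and analysed for every control, evaluation and maintenance cell of Table 4 (24 clinic-periods); IF cells are excluded [or: carry their own fixed term].* Reword the sentence on three primary time points so that it names phases and does not limit this outcome to three windows.
2. Replace 375 and 94 with the requirement for that design: about 143 per clinic-period with IF excluded, or 127 with its own term. With IF excluded, report power at the expected 300 per clinic-period for both contrasts (99.6% for evaluation, above 99.9% for maintenance), with the model and assumptions behind the figures.
3. Reconcile Table 3 with the site list (Boston Medical Center versus the Haelen Center). Recompute the patient-level baseline for receipt of any treatment, medication or counseling, from the actual four sites, and rerun the power with it.

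The cost is wording, record extraction for the additional six-month periods of routinely recorded data, and a baseline count at four clinics. No new patients are needed. The published requirement becomes less favourable, at 143 or 127 instead of 94.
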